Approach: *We will randomize 20 clinics to receive the ATP or no intervention (SOC) and compare disclosure and appropriate transition using pre-specified milestones among a group of children and adolescents with heterogeneous ages. During early implementation, we will monitor fidelity to the intervention using modified plan-do-study-act (PDSA) cycles. We will track implementation outcomes and factors influencing implementation during the initial ATP implementation phase (6 months). During this time, the study team will discuss and support changes to refine the tool as needed at each facility. Following the initial implementation period, HCWs will take part in focus group discussions to share their suggestions for optimizing the transition tool based on their experience. Understanding personal experiences with the tool will provide an opportunity for lessons learned and continued refinement of the intervention. At the end of the study, we will qualitatively evaluate acceptability, appropriateness and feasibility of the ATP by conducting interviews and FGDs with all HCWs from implementing sites and adolescents from a sub-set of intervention sites, purposively selecting to include participants from high and low performing facilities. We will also conduct pre-trial and post-trial surveys with adolescents and HCWs to quantitatively assess acceptability, appropriateness, feasibility of the ATP and implementation intervention fidelity. At 6-monthly intervals, we will collect readiness assessment information from adolescents in participating clinics.*

SECTION 3: STUDY OUTCOMES

Aim 1

- Prevalence of transition
- Age at transition
- Co-factors for retention
- Age at disclosure
- Co-factors of disclosure
- Individual level co-factors of effective transition
- Facility level co-factors of effective transition

Aim 2

- Adapted transition tool

Aim 3

- The primary outcome is **disclosure** among non-disclosed adolescents and **effective transition and transition readiness** among disclosed adolescents

- Disclosure will be defined as no, partial or complete disclosure. Time to disclosure and age at disclosure will also be assessed.
- Effective transition with retention in care will be defined as completing a visit on the adult day or completing a visit without a caregiver and repeat visits continuing for at least 6 months after transition.
- Transition readiness will be defined as change in response to readiness assessment questions administered every 6 months

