Focus group discussions and interviews will be recorded and transcribed verbatim. Transcripts will be coded and thematic analysis will be conducted on the transcripts using ATLAS.ti. At least 2 researchers will independently code the data, coordinating their findings and analyses to create a comprehensive codebook and concept map. Themes related to how to culturally adapt and improve the described transition intervention, and how to improve clinical care for HIV-infected adolescents, will be identified and used to revise the implementation of the intervention.

Aim 3

The primary analysis will be an intent-to-treat (ITT) analysis.

We will use generalized estimating equations (GEE) clustered on facility level to compare differences in age-appropriate disclosure and change in transition readiness over time between control and intervention communities during baseline and intervention periods. In order to decrease variability between our sites and increase precision of our outcome measures, we will control for baseline adolescent disclosure and transition proportions in our models. We hypothesize that the increases in disclosure and transition proportions between the baseline and intervention periods will be greater among intervention than control facilities.

The first 6 months of the intervention will be considered a “catch up” period; while outcomes will be compared during the full study period, a sub-group analysis is planned for the first 6 months to see if the effect of the intervention is greater during the “catch-up” period.

Focus group discussions and interviews will be recorded and transcribed verbatim. Transcripts will be coded and thematic analysis will be conducted on the transcripts using ATLAS.ti. At least 2 researchers will independently code the data, coordinating their findings and analyses to create a comprehensive codebook and concept map. Themes related to implementation acceptability, feasibility, appropriateness and challenges and successes will be identified. Proportions satisfied with the transition and disclosure process will be compared between the 2 arms.

SECTION 12: ETHICS/PROTECTION OF STUDY PARTICIPANTS

COVID-19 ADAPTED STUDY PROCEDURES

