Recruitment Scripts:

Study Activity	Recruitment Script
Aim 1`	
Facility Survey	Facility Survey Recruitment Script
Aim 2	
Adolescents in HIV care (48 not completed transition, 48 transitioned)	NA
	Caregiver recruitment script for adolescent IDI and FGD
	Adolescent recruitment script
Caregivers	Caregiver recruitment script
Policy makers	Policy maker/Admin/HCW recruitment script
HCW/Administrator	Policy maker/Admin/HCW recruitment script
Working group	HCW recruitment script for Workshop
Aim 3	
Pre-Trial surveys	Adolescent Recruitment Script*
Implementation Activities	HCW IS Activities Recruitment Script
Post-trial IDI	NA
	Adolescent recruitment script*
	Caregiver recruitment script*
	HCW recruitment script*
Implementation FGDs	HCW FGD Recruitment Script
Transition readiness	Adolescent recruitment script*
Disclosure readiness	Caregiver recruitment script
Post-trial surveys	Adolescent recruitment script*
	HCW recruitment script*

*Same as aim 2 document

ATTACH STUDY ANALYSIS PLAN (Finalized 2.13.2020)

SUMMARY

Study Purpose: To determine whether an adolescent transition package (with transition and disclosure tools) improves **mean transition readiness** among HIV positive adolescents in care in Kenya.

Study Design: Cluster randomized trial

Study Population and Sites:

Population:

- HIV-positive adolescents and youth between the ages of 10 and 24

Sites:

- 20 HIV clinics in Nairobi, Nakuru, Homabay and Kajiado, Kenya

Study Duration: Estimated 18 months total (enrollment and 1-year follow-up)

Randomization: 10 clinics randomized to intervention sites and 10 to control.

Intervention:

Adolescent Transition Package (ATP): The ATP will consist of a validated disclosure booklet and disclosure tracking tool, and a HCW administered transition booklet and transition tracking logs, implemented in intervention sites. HCW in intervention sites will be trained on implementation of the ATP with continued support for the clinic in the first 3 months of the intervention. In control sites, parallel data collection for primary outcomes will be conducted.

Primary endpoints: Transition readiness

Secondary endpoints: Overall clinic retention and overall viral suppression

Exploratory outcome: % with full disclosure, Time to full disclosure, Post transition retention

DATA ANALYSIS

Primary outcome: transition readiness among HIV positive adolescents age 15-24

- a. Transition readiness score overall (all domains)
- b. Treatment literacy readiness score

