- c. Self-management readiness score
- d. Communication readiness score
- e. Support readiness score

Analysis

Primary analysis ITT: Mixed effects linear regression to compare transition readiness scores (overall and by domain) over time in control and intervention sites with adjustment for multiple testing (Benjamin-Hochberg method).

Time points: Enrollment, month 6, month 12

Sample size and power table

Assumptions: 80% power, alpha 0.05, ICC 0.2, average cluster size of 50

Mean difference	SD	Number of Clusters per Arm
0.5	1	4
0.5	2	15
1.0	2	4
1.0	3	9
1.5	3	4
1.5	4	7
2.0	5	6
2.0	6	9

Secondary outcomes

- a. Overall retention in 10-24 year olds: defined as proportion of 10-24 year olds completing visits within 6 months of last visit
- b. Overall viral suppression: defined as proportion of 10-24 year olds with viral load of less than 1000 copies per ml after at least 6 months of ART

Analysis

Overall retention/suppression: Generalized estimating equations (GEE) to compare retention and viral suppression in intervention and control sites

Time-points: Baseline, month 6, month 12

Minimum detectable differences in proportions with outcomes

Assumption: 80% power, alpha 0.05, ICC 0.2, 10 clusters per arm, average cluster size of 50

Proportion with outcome in arm 1	Proportion with outcome in arm 2
0.2	0.31
0.3	0.44
0.4	0.56

0.5	0.69
0.6	0.81
0.7	0.93

Exploratory analyses

1. Post-transition retention defined as completing and adult clinic visit day after transfer to adult services and at least 1 other visit within 6 months of the adult visit (total of 2 visits):
Analysis: GEE to compare post-transition retention in intervention and control sites
2. Principal components analysis to identify the most representative components of data in the 4 domains of the readiness assessment checklist (HIV treatment literacy (Q 1-5), self-management (Q6, 7, 9-14, communication Q16-19, support 20-22) and then factor analysis to determine the most important components.
3. Proportion of children with full disclosure and time to full disclosure. Children who do not know their HIV status from HCW assessment. Child will be asked why they are taking medicine; if they report they have HIV they have reached full disclosure. If they mention any other illness or other responses they will not have reached full disclosure.
End point: Child says they have HIV in response to the question “why are you taking your medicine”
Analysis: Descriptive %, time to full disclosure

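### Disclosure is an Aim 3 primary outcome in the protocol but exploratory in the SAP, which omits the between-arm disclosure comparison that Section 11b plans; no text reconciles the two

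*Combined protocol and SAP*

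**What the plan says.** **Protocol.** Section 3 states for Aim 3: "The primary outcome is disclosure among non-disclosed adolescents and effective transition and transition readiness among disclosed adolescents". In Section 2b, the first clause of the Aim 3 hypothesis is that the package raises the proportion of children and younger adolescents disclosed to. Section 11a and Table 8 size complete disclosure at 30% against 50%. Section 11b declares an intention-to-treat primary analysis and a GEE clustered on facility to "compare differences in age-appropriate disclosure and change in transition readiness over time between control and intervention communities". It adds that "we will control for baseline adolescent disclosure and transition proportions in our models", and hypothesises that "the increases in disclosure and transition proportions between the baseline and intervention periods will be greater among intervention than control facilities". Sections 6, 7c and 8 give two years of follow-up.

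**SAP (marked finalized 13 February 2020).** The Summary names transition readiness as the only primary endpoint and retention and viral suppression as secondary, then: "Exploratory outcome: % with full disclosure, Time to full disclosure, Post transition retention". Study duration is 18 months in total, including one year of follow-up. In the exploratory list, item 1 (post-transition retention) has a stated contrast, "GEE to compare post-transition retention in intervention and control sites". Item 3 (disclosure) has only "Analysis: Descriptive %, time to full disclosure". No SAP outcome is called effective transition. Appendix 1 schedules the disclosure items and post-transition retention under a secondary-outcome heading, with collection ending at month 12.

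**The concern.** The two documents give different answers to the question of what the trial's primary outcome is. Of the protocol's three Aim 3 primaries, readiness keeps that rank in the SAP, disclosure becomes exploratory, and effective transition does not appear under that name. The SAP is also inconsistent with itself on disclosure: exploratory in the Summary and body, secondary in Appendix 1.

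Two things are at stake. Readers working from different documents could disagree on which result decides the trial. And the disclosure tool is one of the two components of the package (Section 6), yet the SAP contains no between-arm test of whether it raises disclosure. Low rank alone does not explain the omission, because another exploratory outcome in the same list does get a between-arm GEE.

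**Working it through.** **1. The texts side by side**

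| Item | Protocol | SAP |
|---|---|---|
| Disclosure, tier | Primary (Section 3) | Exploratory (Summary, body); secondary (Appendix 1) |
| Disclosure, analysis | Facility-clustered GEE between arms, baseline control (11b) | Descriptive percentage and time to disclosure (item 3) |
| Effective transition | Primary (Section 3) | No outcome of that name; post-transition retention is exploratory, with a GEE |
| Transition readiness | Primary (Section 3) | Sole primary |
| Follow-up | 2 years (Sections 6, 7c, 8) | 1 year (Summary); month 12 (Appendix 1) |

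Neither document says that one hierarchy replaces the other, or why.

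**2. Did the protocol size the disclosure comparison?** Inputs from Section 11a and Table 8: 30% v 50%, m = 100 per clinic, between-cluster coefficient of variation k = 0.3, alpha 0.05 (taken as two-sided), 80% power. The unmatched cluster-trial formula is

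c = 1 + (1.960 + 0.842)² × V / (p0 − p1)², with V = p0(1−p0)/m + p1(1−p1)/m + k²(p0² + p1²).

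V = 0.21/100 + 0.25/100 + 0.09 × (0.09 + 0.25) = 0.0352.

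c = 1 + 7.849 × 0.0352/0.04 = 7.91, so 8 clinics per arm, as Table 8 states. The same formula gives 8.34 for 50% v 80% (stated 9), 6.49 for 10% v 20% (stated 7) and 9.48 for 25% v 15% (stated 10).

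With 10 clinics per arm, power = Φ(√(9 × 0.04/0.0352) − 1.960) = Φ(3.198 − 1.960) = 0.89.

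**3. Can the SAP's sizing inputs be applied to disclosure?** The SAP gives none for disclosure. Its table for the secondary proportions states "Assumption: 80% power, alpha 0.05, ICC 0.2, 10 clusters per arm, average cluster size of 50". Taken literally for 30% v 50%:

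- Design effect = 1 + 49 × 0.2 = 10.8; effective n per arm = 500/10.8 = 46.3.
- SE = √(0.46/46.3) = 0.0997; z = 0.20/0.0997 = 2.006.
- Power = Φ(2.006 − 1.960) = 0.52, or 0.50 with a pooled null variance.

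But that ICC does not reproduce the SAP's own table (80% power, 10 clinics per arm, m = 50):

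| Arm 1 | Arm 2, SAP | Detectable at ICC 0.2 | Detectable at CV 0.2 | Power of SAP row, ICC 0.2 | Power of SAP row, CV 0.2 |
|---|---|---|---|---|---|
| 0.2 | 0.31 | 0.463 | 0.306 | 23% | 83% |
| 0.3 | 0.44 | 0.577 | 0.433 | 29% | 84% |
| 0.4 | 0.56 | 0.679 | 0.558 | 35% | 81% |
| 0.5 | 0.69 | 0.769 | 0.682 | 48% | 83% |
| 0.6 | 0.81 | 0.850 | 0.805 | 62% | 82% |
| 0.7 | 0.93 | 0.919 | 0.928 | 85% | 81% |

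A coefficient of variation of 0.2 fits all six rows; an ICC of 0.2 falls well short on five. With CV 0.2 and m = 50, 30% v 50% has V = 0.0042 + 0.0050 + 0.04 × 0.34 = 0.0228 and power Φ(√(9 × 0.04/0.0228) − 1.960) = Φ(3.974 − 1.960) = 0.98.

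**4. Can the planned GEE be run from the text as it stands?** Not yet, for three reasons.

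- *Denominator.* Section 3 and SAP item 3 point to children who do not know their status; Section 11b describes change in proportions between periods.
- *Age range.* 6–15 (Section 11a text), 10–15 (Table 8), 6–19 and 6–17 (caregiver surveys: Section 7c text, and the Section 7c list with Section 10), 10–24 (SAP Summary).
- *Control-arm data.* Table 3 and Sections 7c and 10 put the disclosure checklist in both arms. The SAP Summary describes parallel collection in control sites for primary outcomes, and its only primary is readiness. Appendix 1 does not split collection by arm.

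**The case against.** **The SAP governs.** It is the dedicated, finalized analysis plan, the protocol's signature page is dated April 2018, and Section 11b is headed an overview. A deliberate change of hierarchy is therefore possible, and if it was made, readiness as sole primary is legitimate. But no text says so. The protocol supplied includes COVID-19 procedures, so it has been revised since signature, and it still keeps disclosure as primary, the GEE and two-year follow-up. Section 3 is not an overview.

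**Descriptive reporting is acceptable for an exploratory outcome.** In general it is, and item 3 does not forbid showing percentages by arm; it is silent. What stands is that the protocol hypothesises, sizes and plans this comparison, and the SAP drops it without comment.

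**Stronger readings that the documents do not support.** A reader might infer that post-transition retention, which needs one further visit within six months, contradicts the protocol's effective transition, which needs visits continuing for at least six months. They are separately named outcomes; the supported point is only that the SAP has no effective-transition outcome. A reader might also infer that disclosure has only about 50% power under the SAP. That figure depends on an ICC label that the SAP's own table does not bear out, in a table for other outcomes. Nor does anything in the documents show that the hierarchy was changed in the light of results.

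**Conclusion.** The point holds and needs correcting before analysis. The two hierarchies conflict, the follow-up horizons differ (24 against 12 months), and the SAP lacks the between-arm disclosure analysis that the protocol plans. These conclusions come from the text and depend on no power figure.

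On size: the protocol's comparison has about 89% power for 30% v 50% with 10 clinics per arm, given CV 0.3, 100 children per clinic and two-sided alpha 0.05. Section 11a also states a 15% control rate, and none of these inputs is specific to children undisclosed at baseline, so 89% confirms that the comparison was sized and does not forecast its power. SAP-based values run from about 50% (literal ICC 0.2) to about 98% (CV 0.2); that spread is a reason to draw no power conclusion from the SAP.

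**What to change.** 1. State one outcome hierarchy and one follow-up horizon in protocol Sections 3 and 11b, the SAP Summary and body, and Appendix 1. If readiness is to be the sole primary, say so in Section 3 with a dated reason. Say whether effective transition is dropped or replaced by post-transition retention.
2. In SAP exploratory item 3, replace the descriptive percentage with the facility-clustered between-arm GEE from Section 11b, adjusted for baseline disclosure proportion, at the tier the sponsor assigns. Name the denominator (children undisclosed at baseline, or change in clinic proportions) and one age range.
3. Reconcile the SAP's statement on control-site data collection with Table 3 and Sections 7c and 10, so that disclosure checklist data from control clinics are secured.

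Optional: a small-sample variance correction for 20 clusters, a clustered time-to-event model for time to disclosure, and a tier and analysis for age at full disclosure, which Appendix 1 schedules but the SAP body does not analyse.

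Cost: wording in both documents and one more clustered model. No new data collection is needed if the protocol's two-arm checklist plan stands; item 3 has to confirm that. The disclosure result may show a smaller effect or less precision because in-person disclosure activities were suspended under the COVID-19 procedures in Section 7.

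### Aim 3 names no small-sample method for 20 clinics, and the SAP leaves its tested term and random effects unwritten; separately, the Aim 1 logistic model names no clinic term

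*Combined protocol and SAP*

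**What the plan says.** **Aim 3, SAP.** The SAP Summary calls the study a "Cluster randomized trial" with 10 clinics per arm. The primary analysis is "Mixed effects linear regression to compare transition readiness scores (overall and by domain) over time in control and intervention sites". It uses the visits at enrollment, month 6 and month 12 and applies a Benjamini-Hochberg correction across the scores. The power table rests on "Assumptions: 80% power, alpha 0.05, ICC 0.2, average cluster size of 50". For the secondary outcomes the SAP gives "Generalized estimating equations (GEE) to compare retention and viral suppression in intervention and control sites".

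**Aim 3, protocol.** Section 11b says "We will use generalized estimating equations (GEE) clustered on facility level" and describes the readiness comparison as "change in transition readiness over time between control and intervention communities during baseline and intervention periods". Section 3 defines the outcome the same way: "Transition readiness will be defined as change in response to readiness assessment questions administered every 6 months". Section 11b also plans adjustment for baseline disclosure and transition proportions, and section 5e allows restricted randomization. Table 3 expects 50-500 clients per clinic.

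**Aim 1, protocol.** Section 11b assigns logistic regression to cofactors of effective transition and mentions no clinic random effect or clustered variance. Section 3 lists facility-level cofactors of effective transition as an outcome, and the section 2b hypothesis names a transition plan and adolescent-friendly services at the facility. Section 11a sizes Aim 1 with an ICC of 0.05, for retention and viral suppression.

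**The concern.** With 10 clinics per arm, the arm comparison rests on about 18 between-clinic degrees of freedom. Large-sample z tests, and the usual sandwich variance in GEE, then understate uncertainty. The Benjamini-Hochberg step does not repair this because it takes the p-values as given.

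The unwritten tested term matters more. Three visits leave open a month-12 difference, an average difference or an arm-by-time term, and the wording in both documents leans towards change. A clinic random intercept cancels out of a change contrast. If clinics drift differently over the year, it gives no protection, and the size of the error depends on a modelling choice the SAP leaves to the analyst.

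In Aim 1, a facility feature is shared by every adolescent in a clinic. A logistic model that treats them as independent can declare such a feature a cofactor by chance more often than 5% of the time.

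**Working it through.** **The plan's own figures.**
- Protocol Table 8 (CV 0.3, 100 per clinic): k = 1 + 7.849 × [p0(1−p0)/100 + p1(1−p1)/100 + 0.09(p0² + p1²)]/(p0−p1)². For 50% v 80%: 1 + 7.849 × 0.0842/0.09 = 8.34, so 9 as printed. The rows 30% v 50%, 10% v 20% and 25% v 15% give 7.91, 6.49 and 9.48, so 8, 7 and 10 as printed. Without the leading 1, each is one lower. The protocol's design therefore did allow for few clusters.
- SAP means table, first row (difference 0.5, SD 1): 2 × (1/0.5)² × 7.849 × DE/50. At ICC 0.2, DE = 10.8 gives 13.56, so 14 against a printed 4. At ICC 0.04, DE = 2.96 gives 3.72, so 4, and all eight rows match. That mismatch is a separate matter. It is why ICC 0.04 appears below as an assumed alternative; the documents do not state it.

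**Difference at one visit, mixed model with clinic intercept, z reference.**
- REML: 2P(t18 > 1.96) = 6.6%.
- ML: 2P(t18 > 1.96 × √0.9) = 7.9%.
- With a t18 reference, simulation gives 5.0%.

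**GEE clustered on clinic, uncorrected sandwich, z reference (simulation, no true effect).**

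| Setting | Uncorrected, z | Kauermann-Carroll, t18 |
|---|---|---|
| Change contrast, 50 per clinic | 7.7-8.0% | 4.9-5.1% |
| Binary, 60-90%, ICC 0.04, 50 per clinic | 7.6-8.4% | 4.6-5.4% |
| Binary, 90%, ICC 0.2, 50 per clinic | 11.2% | 7.8% |
| Binary, 60-80%, sizes log-uniform over 50-500 (assumed), independence working correlation | 10-11% | 6-7% |

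In the last setting, an exchangeable working correlation with the same correction gives 4.6-5.7%.

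**Arm-by-time term with only a clinic intercept at clinic level.** Let ρ be the ICC, r the clinic autocorrelation, s = 0.5 the individual autocorrelation and m = 50. The documents give neither r nor s. Up to a common factor:
- true variance: ρ(1−r) + (1−ρ)(1−s)/m
- model variance: [ρ(1−r) + (1−ρ)(1−s)]/m
- error rate: 2[1 − Φ(1.96/q)], where q is the square root of their ratio

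| ICC | r | True | Model | q | Error |
|---|---|---|---|---|---|
| 0.2 (SAP) | 1 | 0.0080 | 0.0080 | 1.00 | 5.0% |
| 0.2 | 0.95 | 0.0180 | 0.0082 | 1.48 | 19% |
| 0.2 | 0.8 | 0.0480 | 0.0088 | 2.34 | 40% |
| 0.04 (assumed) | 0.95 | 0.0116 | 0.00964 | 1.10 | 7.4% |
| 0.04 | 0.8 | 0.0176 | 0.00976 | 1.34 | 14% |

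A t18 reference cannot correct a standard error that is too small by the factor q. With a clinic-by-time random effect fitted (ICC 0.04; r = 0.8, 0.95, 1), simulation gives 6.3%, 5.1% and 4.1% with REML and z, and 4.8%, 3.7% and 2.9% with t18.

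**Aim 1, facility-level cofactor, unclustered logistic model.** The sample size reproduces: 0.6 × 0.4 × (1.96/0.025)² × 3.45 = 5089, and 5089/50 = 101.8, so 102 clinics. The number of transitioned adolescents per clinic is not given. Applying the 20% transition share from the Aim 3 paragraph of section 11a to 50-147 adolescents per clinic (15,000/102 = 147) gives 10-29. Applying it only to the 20% whom that paragraph treats as eligible gives 2-6. With DE = 1 + (m−1) × 0.05 and error 2[1 − Φ(1.96/√DE)]:

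| m | DE | Error |
|---|---|---|
| 2 | 1.05 | 5.6% |
| 6 | 1.25 | 8.0% |
| 10 | 1.45 | 10% |
| 29 | 2.40 | 21% |

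At ICC 0.01, m = 10-29 gives 6-8%. With clinic-clustered variance and ICC 0.05, simulation gives 5.1% at m = 10 and 5.7% at m = 29.

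**The case against.** The strongest reply is that the trial is openly cluster randomized, the protocol clusters its GEE on facility, the power tables carry an ICC or CV, and a competent analyst would fit clinic effects with suitable degrees of freedom. Much of this stands. A reader might infer from the one-sentence model that clinics are ignored altogether, which would give about 55% error at ICC 0.2 for a simple comparison of scores. The documents do not support that reading, because mixed effects in a cluster trial powered with an ICC imply a clinic term. Nor was the small number of clusters overlooked in the protocol's design, as Table 8 shows.

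The z reference and the choice of ML or REML are assumptions, since no software or default is stated. The 6.6% and 7.9% apply to a difference at one visit and should not be carried over to a change test, which holds 5% with a clinic intercept if clinics do not drift. The drift figures rest on assumed autocorrelations. Baseline adjustment and restricted randomization would change both the error rate and the degrees of freedom, and they are not in these calculations.

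On Aim 1, section 11b is an overview and its example cofactors are individual-level. The 20% share is borrowed from Aim 3 and the ICC from other outcomes. A reader might infer that all Aim 1 regressions are invalid. The figures do not extend to individual-level cofactors and were not computed for the Cox models.

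What remains is the omission itself: a SAP is where the tested term, the random effects and the small-sample method are fixed in advance.

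**Conclusion.** The point holds as an under-specification that should be repaired before analysis; it is not a finding that clustering is ignored. For the protocol's GEE and the SAP's secondary GEE, the usual default runs moderately above nominal, at about 8% with equal clinics and 10-11% with sizes spread over the range in Table 3. For the SAP's primary model the outcome depends on what is tested: 6.6-7.9% for a difference at one visit with z. For a change test with a clinic intercept only, it is anywhere from 5% (no drift) to 19-40% at the stated ICC under the assumed drift. The change test is the larger risk, and a t reference alone does not remove it.

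Aim 1 is a separate and smaller point. It is confined to facility-level cofactors, and 5.6-21% is one range governed by an unstated count per clinic.

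**What to change.** **SAP primary model.** Name one tested term. Fit clinic and participant random intercepts, and add a clinic-by-time random effect if change is tested. Use REML with Kenward-Roger or similar degrees of freedom. Reconcile this with the GEE that protocol section 11b assigns to readiness.

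**GEE analyses.** State clustering on clinic, an exchangeable working correlation, a bias-corrected sandwich (for example Kauermann-Carroll) and a t reference with df = 20 minus the number of clinic-level parameters. That is 18 with arm only, and fewer if baseline clinic proportions or restricted-randomization factors are adjusted for. Another named method valid for 20 unequal clusters would also serve.

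**Aim 1.** Use clinic-clustered robust variance or a clinic random effect wherever facility-level cofactors are tested.

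**Cost.** The change is to wording and software options. Aim 3 intervals widen by about 7% (2.101/1.960 = 1.072, REML with z to t18) or 13% (1.072/√0.9 = 1.130, uncorrected GEE with z to corrected with t18). The detectable difference at ICC 0.2 rises from 0.58 to 0.62 SD. The four Table 8 rows checked keep 82-95% power at 100 per clinic. The clinic-by-time model with t18 is conservative if clinics do not drift (2.9%), and the GEE correction stays incomplete for outcomes near 90% with a high ICC. Aim 1 facility-level intervals widen by √DE, about 1.02 to 1.55 times over 2-29 per clinic, which is their correct width.

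### Five primary readiness scores are adjusted together, but the cluster table is powered for one test at 0.05 and no score or success rule decides the trial

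*Combined protocol and SAP*

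**What the plan says.** In the SAP, under Data Analysis, the heading "Primary outcome: transition readiness among HIV positive adolescents age 15-24" covers five lettered items: "Transition readiness score overall (all domains"), "Treatment literacy readiness score", "Self-management readiness score", "Communication readiness score" and "Support readiness score". The primary intention-to-treat analysis fits mixed effects linear regression to the overall and domain scores "with adjustment for multiple testing (Benjamin-Hochberg method"). No false-discovery level is given.

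The sample size table directly below carries one line of inputs: "Assumptions: 80% power, alpha 0.05, ICC 0.2, average cluster size of 50". It has eight pairs of mean difference and SD, each with a number of clusters per arm. It does not say which score it refers to, how many tests are planned, or which row is the design case. The SAP Summary gives 10 clinics per arm.

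The Summary states a single purpose, better mean transition readiness, and the data collection schedule in Appendix 1 has one primary outcome line. Nothing says whether success means a positive overall score, any positive score, or all five.

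**The concern.** Under a five-test Benjamini-Hochberg procedure the overall score is not simply compared with 0.05. Its threshold lies between 0.01 and 0.05, depending on how many domain p-values are also small. A table computed for one test at 0.05 does not describe that procedure.

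Two things are at stake. The first is power for the question that the SAP sets itself, whether overall readiness improves. The second is interpretation: if the overall score misses and one domain passes, the present text would allow the trial to be reported as either a success or a failure.

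**Working it through.** **Inputs.** From the SAP: alpha 0.05, power 80%, ICC 0.2, m = 50 per cluster, the eight table rows, 10 clusters per arm, five primary scores. Assumed, because not stated: two-sided tests, Benjamini-Hochberg level 0.05, no gain from repeated measures.

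**1. The plan's own table.** Clusters per arm = 2 × [SD × (z_alpha + z_power) / difference]² × [1 + (m − 1) × ICC] / m, with z values 1.960 and 0.842.

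For difference 1.0 and SD 2, the first part is 2 × (2 × 2.802)² = 62.8.
- ICC 0.2: 62.8 × 10.8 / 50 = 13.6, so 14 clusters. The table says 4.
- ICC 0.04: 62.8 × 2.96 / 50 = 3.7, so 4 clusters.

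| Difference / SD | SAP table | ICC 0.2 | ICC 0.04 |
|---|---|---|---|
| 0.5 / 1 | 4 | 14 | 4 |
| 0.5 / 2 | 15 | 55 | 15 |
| 1.0 / 2 | 4 | 14 | 4 |
| 1.0 / 3 | 9 | 31 | 9 |
| 1.5 / 3 | 4 | 14 | 4 |
| 1.5 / 4 | 7 | 25 | 7 |
| 2.0 / 5 | 6 | 22 | 6 |
| 2.0 / 6 | 9 | 31 | 9 |

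The table does not follow from ICC 0.2. At two-sided 0.05 all eight rows match for any ICC from 0.0374 to 0.0405. They also match at alpha 0.01 with an ICC of 0.0185 to 0.0205, so the counts alone do not prove which alpha was used. The stated alpha is 0.05, and I take it as such.

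**2. Thresholds under the adjustment.** With five ordered p-values, Benjamini-Hochberg at 0.05 rejects the k smallest for the largest k whose k-th p-value is at or below 0.05 × k / 5. The possible thresholds are 0.01, 0.02, 0.03, 0.04 and 0.05. A test with 80% power at 0.05 has power Phi(2.802 − z) at each:

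| Threshold | 0.01 | 0.02 | 0.03 | 0.04 | 0.05 |
|---|---|---|---|---|---|
| Power | 58.9% | 68.3% | 73.6% | 77.3% | 80.0% |

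Keeping 80% at 0.01 would need (2.576 + 0.842)² / (1.960 + 0.842)² = 1.49 times the clusters.

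**3. Power of the procedure.** I simulated four correlated domain z-scores and their standardised sum as the overall score, scaled to 80% power at 0.05, with Benjamini-Hochberg across all five (400,000 draws).

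| Domain correlation, equal effects | 0.2 | 0.4 | 0.6 | 0.8 |
|---|---|---|---|---|
| Overall score declared | 64.8% | 67.1% | 69.6% | 71.9% |

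The chance that at least one score is declared is 69-74% in these cases. If one domain carries the whole effect, the overall score is declared about 68% of the time. A different model, five separate scores of which one to five have equal effects, gives 59-77% for a given score. Every case is below 80%.

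**4. What that means with 10 clusters per arm.** At ICC 0.04 the effective sample per arm is 500 / 2.96 = 168.9. For difference 1.0 and SD 3, the standard error is 3 × √(2 / 168.9) = 0.326 and the ratio is 3.06. Power is Phi(3.06 − 1.96) = 86.5% at 0.05 and Phi(3.06 − 2.576) = 68.7% at 0.01. The adjusted column uses the model of step 3, with correlation 0.2-0.6 except where noted.

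| Rows | One test at 0.05 | At 0.01 | Overall score, adjusted |
|---|---|---|---|
| 0.5/1, 1.0/2, 1.5/3 | 99.6% | 97.8% | 98.5-99% |
| 2.0/5 | 95.7% | 86.4% | 89-92% |
| 1.5/4 | 93.1% | 80.8% | 85-88% |
| 1.0/3, 2.0/6 | 86.5% | 68.7% | 74-80% (correlation 0.2-0.8) |
| 0.5/2 | 63.2% | 39.0% | already below 80% |

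At ICC 0.2 as written, no row reaches 80% with 10 clusters per arm even for one test at 0.05 (22-67%).

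**5. Error rates.** The procedure never rejects a score with p above 0.05, so the overall score's own error cannot exceed 0.05. With no effect anywhere, its simulated error was 1.4-3.0% and the family-wise error 3.3-4.8%. With one truly affected domain, the chance of declaring at least one of the three unaffected domains was 7.5%, 6.9% and 6.3% at correlation 0.2, 0.4 and 0.6.

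**The case against.** Adjusting five pre-specified scores together is a legitimate design. The SAP places the domains inside the primary outcome, so calling them secondary is a choice and not a correction. That stands, and it is why a second remedy is offered below.

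The table gives clusters needed for 80% power, while the trial has 10 per arm and seven of the eight rows need 9 or fewer. That also stands. A reader might infer that this trial has only 65-72% power, or that it needs 1.49 times as many clinics. The documents do not support either: no row is the design case, and most rows have slack at an ICC of about 0.04. The 59% figure is a bound, reached only when the overall score is in effect the lone rejection.

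If success meant any positive score, power could be higher. It approaches 100% when one domain carries everything, but that needs a domain effect some 7 to 9 standard errors from zero at correlation 0.2-0.6. With equal effects it is only 69-74% when the overall score has 80% on its own. The SAP does not adopt this rule in any case.

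A reader might also infer that false-discovery control inflates the error of the main claim. It does not. The excess concerns false claims about individual domains when other scores truly differ.

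**Conclusion.** The mismatch is real: five scores tested under Benjamini-Hochberg, a cluster table for one test at 0.05, and no deciding score or success rule. The stated 80% is not the power of the planned test. From exactly 80%, the overall score drops to about 65-72%, given level 0.05, two-sided tests, equal domain effects and domain correlation 0.2-0.8.

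The loss in this trial cannot be fixed from the documents, which give neither the domain correlations nor a design effect. At 10 clusters per arm and an ICC of about 0.04, it takes only the two 9-cluster rows from above 80% to about 74-80%. The inconsistency is certain; the size is conditional. The ICC problem is a separate and larger fault in the same table, and aligning alpha will not by itself make the 80% true.

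**What to change.** First settle the ICC: correct the stated 0.2 if another value or another measure of between-clinic variation was meant, or recompute the cluster counts at 0.2.

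Then name the overall readiness score as the sole primary outcome, tested at two-sided 0.05. List the four domain scores as secondary, with Benjamini-Hochberg across those four at a stated level. This matches the single purpose in the Summary and the alpha in the table. It costs only SAP wording. The downside is that a positive result in a single domain can no longer be claimed as primary.

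If all five scores are to stay primary, state the false-discovery level and what counts as success (overall, any or all), and restate power for that rule with assumed domain correlations and a named design row.
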